8.3. Safety Assessments

Planned timepoints for all safety assessments, including assessments for PVR, are provided in the Schedule of Assessments (Section 1.3). Immediate safety concerns should be discussed with the Sponsor's designated Medical Monitor immediately upon occurrence or awareness to determine if the subject should continue or discontinue study drug.

8.3.1. Vital Signs

Vital signs, including blood pressure, heart rate (by pulse), body temperature, and weight, will be assessed at the timepoints specified in the Schedule of Activities and Section 10.7 as follows:

- Blood pressure and pulse will be measured after the subject has been resting in a seated position for 5 minutes, after PRO assessments and before blood draws.
- Blood pressure measurements will be taken on the same arm and by the same site staff throughout the study, if possible.
- Sitting systolic and diastolic blood pressures will be determined by averaging 3 replicate measurements obtained approximately 1 to 2 minutes apart. The average of the 3 measurements will be used for eligibility and safety assessments.
- The same method for assessing temperature should be used at all visits for a particular subject.
- Body weight will be measured with subjects in street clothing with jacket/coat and shoes removed, using the same scale throughout the study, if possible.

8.3.2. Physical Examinations

Brief physical examinations will include examination of the heart, lungs, abdomen, and visual pelvic examination. In addition, any organ system in which a previous abnormality was noted at Baseline or a subject has a complaint or AE will be examined.

8.3.3. Post-Void Residual Volume

The volume of urine that remains in the bladder after voiding (PVR) is an objective measurement that may serve as a proxy for impaired ability to void. The physician should assess subjects with an increase in PVR volume to determine whether an AE should be reported. (Refer to Section 8.4.6 for additional information on reporting AEs of urinary retention associated with increased PVR.)

The PVR assessment will be performed via ultrasound at the visits indicated in the Schedule of Assessments (Section 1.3). All efforts will be made to ensure the same device and operator are used for all PVR volume measurements for individual subjects.

8.3.4. Clinical Safety Laboratory Assessments

All protocol-required laboratory assessments must be conducted in accordance with the laboratory manual and the Schedule of Assessments. See Section 10.2 for the list of clinical laboratory tests to be performed and the Schedule of Assessments for the timing and frequency. Repeat or unscheduled samples may be taken for safety reasons or for technical issues with the samples.

The clinical significance of test results will be evaluated as follows:

- At Week 24 of Study URO-901-3005, the investigator or physician subinvestigator will assess the clinical significance of any values outside the reference ranges provided by the laboratory, and subjects with abnormalities judged to be clinically significant will be excluded from the study.
- The investigator or physician subinvestigator must review the laboratory report, document this review, and record any clinically relevant changes occurring during the study in the AE section of the eCRF. The laboratory reports must be filed with the source documents. Laboratory abnormalities associated with the underlying disease are not considered clinically significant unless judged by the investigator to have worsened or be more severe than expected for the subject's condition.
- All laboratory tests with values considered clinically significant during participation in the study or within 21 days after the last dose of study drug should be repeated until the values return to normal or baseline or are no longer considered clinically significant by the investigator or the Sponsor's designated Medical Monitor.
 - If such values do not return to normal/baseline within a period of time judged reasonable by the investigator, the etiology should be identified and the Sponsor's designated Medical Monitor notified.
 - If laboratory values from nonprotocol specified laboratory assessments performed at the institution's local laboratory require a change in subject management or are considered clinically significant by the investigator (eg, SAE or AE or dose modification), then the results must be recorded in the eCRF.

8.4. Adverse Events and Serious Adverse Events

The definitions of an AE or SAE can be found in Section 10.3.

AEs will be reported by the subject (or, when appropriate, by a caregiver, surrogate, or the subject's legally authorized representative).

The investigator and any qualified designees are responsible for detecting, documenting, and recording events that meet the definition of an AE or SAE and remain responsible for following up AEs that are serious, considered related to the study drug or study procedures, or that caused the subject to discontinue the study drug or the study (see Section 7).

8.4.1. Time Period and Frequency for Collecting Adverse Event and Serious Adverse Event Information

All AEs and SAEs will be collected from the signing of the informed consent form through the end of study. In addition, any AEs and SAEs reported within 21 days after the last dose of study drug (5 half-lives of vibegron [half-life approximately 80 hours]) will also be collected. AEs will be collected at the timepoints specified in the Schedule of Assessments (Section 1.3), and as observed or reported spontaneously by study subjects.

Medical occurrences that begin before the start of study drug, but after obtaining informed consent will be recorded in the AE section of the eCRF.

All SAEs (including serious AESIs) will be recorded and reported on the eCRF within **24 hours** of the study site personnel's knowledge of the event, as indicated in Section 8.4.4. Marking the event as "serious" will automatically send required notifications for Sponsor or designee review. The investigator will also submit any updated SAE data within 24 hours of receipt of the information. Nonserious AESIs will be reported on the eCRF within **72 hours** of the site's knowledge of the information

Investigators are not obligated to actively seek AE or SAE information after conclusion of the study participation. However, if the investigator learns of any SAE, including a death, at any time after a subject has been discharged from the study, and he/she considers the event to be reasonably related to the study drug or study participation, the investigator must promptly notify the Sponsor or designee.

The method of recording, evaluating, and assessing causality of AEs and SAEs and the procedures for completing and transmitting SAE reports are provided in Section 10.3.

8.4.2. Method of Detecting Adverse Events and Serious Adverse Events

Care will be taken not to introduce bias when detecting AEs and SAEs. Open-ended and non-leading verbal questioning of the subject is the preferred method to inquire about AE occurrences.

8.4.3. Follow-up of Adverse Events and Serious Adverse Events

After the initial AE or SAE report, the investigator is required to proactively follow each subject at subsequent visits/contacts. All AEs will be followed until approximately 21 days after the last dose of study drug. All SAEs will be followed until resolution, stabilization, the event is otherwise explained, or the subject is lost to follow-up (as defined in Section 7.3). If a subject dies during participation in the study or within 21 days of the last dose of study drug, the investigator will provide the Sponsor or designee with a copy of any postmortem findings including histopathology.

The investigator is obligated to perform or arrange for the conduct of supplemental measurements and/or evaluations as medically indicated or as requested by the Sponsor or designee to elucidate the nature and/or causality of the AE or SAE as fully as possible. This may include additional laboratory tests or investigations, histopathological examinations, or consultation with other health care professionals.

New or updated information will be recorded in the originally completed eCRF. As noted above, the investigator will submit any updated SAE data to the Sponsor or designee within 24 hours of receipt of the information.

8.4.4. Regulatory Reporting Requirements for Serious Adverse Events

- Prompt notification of an SAE by the investigator to the Sponsor or designee is essential so that legal obligations and ethical responsibilities towards the safety of subjects and the safety of a study drug under clinical investigation are met.
- The Sponsor has a legal responsibility to notify both the local regulatory authority and other regulatory agencies about the safety of a study drug under clinical investigation. The Sponsor will comply with country-specific regulatory requirements relating to safety reporting to the regulatory authority, IRBs/IECs, and investigators.
- Investigator safety reports must be prepared for suspected unexpected serious adverse reactions (SUSARs) according to local regulatory requirements and Sponsor policy and forwarded to investigators as necessary.
- An investigator who receives an investigator safety report describing an SAE or other specific safety information (eg, summary or listing of SAEs) from the Sponsor or designee will review and then file it and will notify the IRB/IEC/REB, if appropriate according to local requirements.

8.4.5. Disease-Related Events and/or Disease-Related Outcomes Not Qualifying as Adverse Events or Serious Adverse Events

No disease-related events or outcomes are excluded from AE reporting. Any worsening of OAB or BPH symptoms or any events of bladder obstruction should be collected as AEs.

8.4.6. Adverse Events of Special Interest

Selected nonserious and SAEs will be reported as AESIs. AESIs that also meet the definition of an SAE must be reported as described in Section 10.3.

Adverse events of special interest for this study include:

- Adverse events consistent with urinary retention
 - An AE of urinary retention should only be recorded when a subject has a raised PVR that requires intervention with clean intermittent catheterization (CIC) or temporary placement of a urinary catheter according to the following criteria:
 - a) subject has a PVR of ≥ 300 mL (regardless of symptoms), OR

b) subject has a PVR ≥ 200 mL and < 300 mL and the subject reports associated symptoms, ie, sensation of bladder fullness or inability to void despite persistent effort, that in the investigator's opinion require CIC.

Note: An AE of residual urine volume should be recorded if, in the investigator's opinion, the raised PVR is clinically significant but does not fulfill the above definition for urinary retention. As stated above in Section 7, subjects with a single PVR volume of ≥ 300 mL or an AE of urinary retention will be withdrawn from the study.

- Adverse events suggestive of cystitis or urinary tract infection (UTI)
 - An AE of UTI will be recorded if both the following criteria are fulfilled, regardless of subject symptoms:
 - a) a positive urine culture result with a bacteriuria count of $\geq 10^5$ CFU/mL
 - b) leukocyturia of ≥ 5 /hpfIf a subject meets the criteria for the definition of a UTI, the investigator will record whether the UTI was “symptomatic” or “asymptomatic” on the AE eCRF.

Note: If urinalysis/culture results are reported which, in the opinion of the investigator, are considered clinically significant but do not fulfill the above definition of a UTI, the findings should be recorded as AEs (eg, bacteriuria, leukocyturia).

- Potential major cardiac and cerebrovascular events, including death (or any event with fatal outcome), myocardial infarction, cerebrovascular accident, hospitalization for unstable angina or chest pain, hospitalization for heart failure requiring hospitalization, and coronary revascularization/angioplasty/stent
- Hypertension, defined as follows:
 - For subjects with systolic blood pressure < 140 mmHg and diastolic blood pressure < 90 mmHg at the Study URO-901-3005 baseline assessment, the average of 3 systolic blood pressures ≥ 140 mmHg or diastolic blood pressures ≥ 90 mmHg (or both) at any 2 consecutive visits after baseline
 - For subjects with systolic blood pressure ≥ 140 mmHg or diastolic blood pressure ≥ 90 mmHg at Study URO-901-3005 baseline, an increase compared to baseline at 2 consecutive visits in the average of 3 systolic blood pressures by ≥ 20 mmHg or 3 diastolic blood pressures by ≥ 10 mmHg
 - Initiation or increase in dose of medication for treatment of hypertension in any subject
- Adverse events consistent with orthostatic hypotension as confirmed by orthostatic vital signs

- Elevated serum aspartate aminotransferase (AST) or alanine aminotransferase (ALT) lab value requiring that study drug be temporarily withheld or permanently discontinued (see Section 8.4.6.1 and 8.4.6.2). To date, no concern regarding drug-induced liver toxicity has been identified; however, the Sponsor is monitoring laboratory data for a potential safety signal, consistent with Food and Drug Administration guidance [[FDA Guidance, 2009](#)].
- Neoplasms

Serious AESIs and elevated liver enzymes or bilirubin requiring withholding of study drug (see Section 8.4.6.1) must be reported within 24 hours of the study site personnel's knowledge of the event by marking the appropriate box on the AE eCRF and assigning the most appropriate category. Additional information should be provided as directed in the eCRF Completion Guidelines. AESIs that also meet the definition of an SAE must be reported as an SAE, as described in Section 8.4.4. Nonserious AESIs should be reported within 72 hours of the site personnel's knowledge, using the AE eCRF.

8.4.6.1. Criteria for Temporary Withholding of Study Treatment in Association with Liver Test Abnormalities

Elevated liver enzymes or bilirubin sufficient to require withholding study medication must be reported **within 24 hours of the study site personnel's knowledge of the event** using AESI specific eCRFs/forms/worksheets provided for the study.

Hepatic enzymes will be monitored in accordance with FDA drug-induced liver injury guidelines [[FDA, 2009](#)].

If **any** of the following liver test abnormalities develop, Study Treatment should be withheld immediately with appropriate clinical follow-up (including repeat laboratory tests, until a subject's laboratory profile has returned to normal/baseline status), and the event reported as an SAE:

- ALT or AST > 8 x upper limit of normal (ULN)
- ALT or AST > 5 x ULN and persists for more than 2 weeks
- ALT or AST > 3 x ULN and total bilirubin > 2 x ULN or international normalized ratio (INR) > 1.5
- ALT or AST > 3 x ULN with appearance of fatigue, nausea, vomiting, right upper quadrant pain or tenderness, fever, rash and/or eosinophilia (> 5%)

Rechallenge may be considered if an alternative cause for the abnormal liver tests (ALT, AST, total bilirubin) is discovered and the laboratory abnormalities resolve to normal or baseline values. The investigator and Sponsor's designated Medical Monitor must discuss and agree with any decision to rechallenge.

Rechallenge should not occur when the etiology of the liver test abnormalities is considered possibly drug induced.

8.4.6.2. Criteria for Permanent Discontinuation of Study Treatment in Association with Liver Test Abnormalities

Study treatment should be discontinued permanently if **all** of the following 4 criteria are met (ie, potential severe drug-induced liver injury/Hy's law case):

- Total bilirubin increases to $> 2 \times$ ULN or INR > 1.5 **and**
- AST or ALT increases to $\geq 3 \times$ ULN **and**
- Alkaline phosphatase value does not reach $2 \times$ ULN **and**
- No alternative cause explains the combination of the above laboratory abnormalities; important alternative causes include, but are not limited to the following:
 - Hepatobiliary tract disease
 - Viral hepatitis (eg, hepatitis A/B/C/D/E, Epstein-Barr virus)
 - Exposure to hepatotoxic agents/drugs or hepatotoxins, including herbal and dietary supplements, plants, and mushrooms
 - Alcoholic hepatitis
 - Non-alcoholic steatohepatitis
 - Autoimmune hepatitis

If an alternative cause for hepatotoxicity is identified, then it should be determined (based on the severity of the hepatotoxicity or event) whether study drug should be withheld or permanently discontinued as appropriate for the safety of the subject, following consultation with the Sponsor's designated Medical Monitor.

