2.4.2. Potential Risks

The initial clinical program for vibegron in the treatment of OAB includes subjects of both sexes. It is estimated that the ongoing Phase 3 program in OAB (RVT-901-3003 and RVT-901-3004) will include approximately 15% males, which will contribute to safety data comprising more than 200 men in addition to those enrolled in the URO-901-3005 and URO-901-3006 studies.

Based on aggregate preclinical, clinical pharmacology, and Phase 2 and 3 studies, AEs of special interest (AESIs) predefined for specific evaluations in vibegron clinical studies are as follows:

- Potential major cardiovascular events
- Hypertension
- AEs suggestive of orthostatic hypotension as confirmed by orthostatic vital signs
- AEs suggestive of cystitis or urinary tract infection
- Elevated aspartate transaminase (AST) or alanine transaminase (ALT) laboratory value requiring that the study drug be temporarily withheld or permanently discontinued
- Neoplasm

In addition, the risk for increases in post void residual urine volume and urinary volume will be closely monitored for post-void retention during the study. Study URO-901-3005 enrollment criteria will exclude men with PVR volume ≥ 100 mL at screening and at baseline and those with maximum urinary flow (Q_{max}) less than 5 mL/second. Post-void residual urine volume will be assessed throughout the study, and subjects with a single PVR volume of ≥ 300 mL or an AE of urinary retention will be withdrawn.

Prespecified definitions of urinary retention and other AESIs are provided in the Adverse Event of Special Interest section (Section 8.4.6). More detailed information about the known and expected benefits and risks from the study and reasonably expected AEs of vibegron may be found in the Investigator's Brochure.

[figure not shown]
3. Objectives and Endpoints

Assessments in Study URO-901-3006 are referenced to the initial Baseline (Visit 3) from Study URO-901-3005. Therefore, CFB study endpoints for Study URO-901-3006 are relative to Study URO-901-3005 baseline. At the Week 52 visit, CFB comprises 52 weeks of vibegron exposure for subjects randomized to vibegron in Study URO-901-3005 and 28 weeks of vibegron exposure for subjects randomized to placebo.

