- TEAE of Special Interest (by protocol-defined AESI category);
- Treatment-Related TEAE of Special Interest (by protocol-defined AESI category);
- Non-fatal TEAEs;
- Hypertension TEAEs by Pre-existing Hypertension (Yes vs No) and Baseline Hypertension (Yes vs. No). Hypertension TEAEs will be selected as any TEAE with a preferred term of Hypertension.

In addition, a summary of all TEAEs by PT occurring in at least 2% of subjects will be created and ordered by descending overall frequency.

Adverse events of special interest for this study include:

- Adverse events consistent with urinary retention
- Adverse events suggestive of cystitis or urinary tract infection (UTI)
- Potential major cardiac and cerebrovascular events, including death (or any event with fatal outcome), myocardial infarction, cerebrovascular accident, hospitalization for unstable angina or chest pain, hospitalization for heart failure requiring hospitalization, and coronary revascularization/angioplasty/stent
- Adverse events consistent with hypertension (see protocol section 8.4.6)
- Adverse events consistent with orthostatic hypotension as confirmed by orthostatic vital signs
- Elevated serum aspartate aminotransferase (AST) or alanine aminotransferase (ALT) lab value requiring that study drug be temporarily withheld or permanently discontinued
- Neoplasms

Treatment listings will include the planned treatment duration, start and stop dates/times of the AE, study day (relative to start of double-blind treatment on URO-901-3005) and treatment day (relative to the day of first dose of vibegron). A treatment related AE is defined as an AE for which the investigator classifies the AE as being “Probably Related” or “Possibly Related” to study treatment on the Adverse Event CRF. Missing relationship and severity (intensity) will be imputed per Section 4.2.3.

The following additional listings will be provided:

- Listing of Deaths
- Listing of Serious TEAEs
- Listing of Treatment-Emergent AESIs
- Listing of TEAEs Leading to Withdrawal or Interruption of Study Treatment
- Listing of all AEs with a flag for TEAEs and onset (Prior = prior to first dose of vibegron or Treatment = on or after first dose of vibegron.)
- Listing of all medical history including pre-treatment adverse events with coded preferred terms in the hypertension AE search list:
 - Accelerated hypertension
 - Diastolic hypertension
 - Essential hypertension
 - Hypertension

- Hypertensive crisis
- Hypertensive emergency

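### Protocol 8.4.6 does not settle whether a PVR of 300 mL or more without a need for catheter intervention is a urinary retention AESI, and no planned SAP table can recover the count

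*Protocol*

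**What the plan says.** Protocol 8.4.6 opens the retention AESI with a recording rule: "An AE of urinary retention should only be recorded when a subject has a raised PVR that requires intervention with clean intermittent catheterization (CIC", which continues "or temporary placement of a urinary catheter according to the following criteria". Two criteria follow:

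- (a) "subject has a PVR of ≥ 300 mL (regardless of symptoms), OR"
- (b) a PVR from 200 mL to below 300 mL, with reported symptoms "that in the investigator's opinion require CIC".

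A Note supplies another term, an AE of residual urine volume, for cases where the investigator considers that "the raised PVR is clinically significant but does not fulfill the above definition for urinary retention". The same Note repeats the withdrawal rule: "subjects with a single PVR volume of ≥ 300 mL or an AE of urinary retention will be withdrawn from the study". Protocol 2.4.2 and 7.1 name the same two triggers. Protocol 8.3.3 leaves it to the physician whether a PVR increase is an AE, and refers back to 8.4.6. Under Protocol 8.4.1, nonserious AESIs are due on the eCRF within 72 hours.

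SAP 7.3 gives the category by name only, "Adverse events consistent with urinary retention", and summarises AESIs by the protocol's categories. SAP 7.7 tabulates PVR as below 100, 100 to below 200, 200 to below 350, and 350 mL or more, and lists all values.

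**The concern.** The lead-in makes a need for catheter intervention a condition for recording retention. Criterion (a) then sets a volume threshold and is silent on catheters, while criterion (b) states the catheter condition again. If the lead-in governs both criteria, its repetition in (b) is redundant. If (a) and (b) themselves define when intervention is required, a PVR of 300 mL or more qualifies alone, and the word *only* in the lead-in does less than it appears to.

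Long-term safety is the primary objective, and the synopsis gives urinary retention as its example of this population's particular safety needs. An AESI count that depends on how a sentence is parsed is hard to interpret when few events are expected, and the SAP adds no rule that would make it uniform.

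**Working it through.** The plan states no figure on this point, so there is none to reproduce. The check is to write each reading as a rule, see where they part, and ask whether another section or a planned table closes the gap.

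**Step 1: the two rules.**

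- R1 (criteria define the need): PVR ≥ 300 mL; or PVR 200 to < 300 mL with symptoms requiring CIC.
- R2 (lead-in is an extra condition): catheter intervention required, and either PVR ≥ 300 mL or PVR 200 to < 300 mL with symptoms.

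**Step 2: example patients** (values chosen for illustration).

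| PVR | Symptoms | Intervention required | R1 | R2 |
|---|---|---|---|---|
| 320 mL | no | no | yes | no |
| 320 mL | yes | no | yes | no |
| 320 mL | no | yes | yes | yes |
| 250 mL | yes | yes | yes | yes |
| 250 mL | yes | no | no | no |

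The rules differ only for PVR ≥ 300 mL with intervention judged not required.

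**Step 3: does another section decide?** The withdrawal rule lists a PVR of 300 mL or more and a retention AE separately. That fits R2. It also fits R1, because criterion (b) can produce a retention AE below 300 mL, so the second trigger is needed under either rule. Protocol 8.3.3 points back to 8.4.6, and SAP 7.3 inherits the protocol's definition. None of these decides it.

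**Step 4: can a planned table recover the count?**

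- SAP 7.7 puts 300 to 349 mL in the same category as 200 to 299 mL.
- SAP 4.2.4.2 keeps one record per window for by-visit displays, the one closest to the nominal day. Suppose a man has Visit 13 on Day 253 and an unscheduled reading of 320 mL on Day 290. Both fall in the window [225, 308]. The distances are 253 − 253 = 0 and 290 − 253 = 37 days, so the 320 mL reading is not displayed.
- SAP 4.2.2 admits unscheduled values to any-time on-treatment endpoints, but SAP 7.7 defines none for PVR.

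Only the listing isolates every value of 300 mL or more.

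**Step 5: scale.** The documents give no rate for the disputed patients. With N = 300 (Protocol 9.7) and k such men, assumed to be 1, 3 or 6, the shift is k/300. The intervals are exact (Clopper-Pearson) 95% limits, for the case in which these men are the only candidates and every site uses the same rule.

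| k | Shift (percentage points) | R2 | R1 |
|---|---|---|---|
| 1 | 0.33 | 0/300 (0 to 1.22%) | 1/300 (0.01 to 1.84%) |
| 3 | 1.0 | 0/300 (0 to 1.22%) | 3/300 (0.21 to 2.89%) |
| 6 | 2.0 | 0/300 (0 to 1.22%) | 6/300 (0.74 to 4.30%) |

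**The case against.** The best defence is that the sentence, read whole, favours R2. *Only* makes intervention a necessary condition, the criteria then set thresholds within it, and criterion (a) waives symptoms, not intervention. On this view the disputed man has a place already, since the Note provides residual urine volume as the term for him. This has force as the more literal reading. It does not explain why (b) states the catheter condition again and (a) does not, so it does not settle the matter.

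Much of the rest of the defence stands:

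- The man is withdrawn under either reading, so he appears in disposition, and his PVR is listed. If the rise is recorded as an AE leading to discontinuation, he is in that table too. A reader might infer that such cases would vanish from the safety report; the documents do not support that.
- A reader might infer that sites are already counting differently. Divergence is a foreseeable result of the wording, not something the documents show. Protocol 8.4.6 refers to eCRF Completion Guidelines, which are not among the documents reviewed and might address it.
- A reader might infer from the separate withdrawal triggers that 300 mL alone is not retention. Step 3 shows that they fit both readings.
- A reader might take the test to be whether the man was catheterised. The text asks whether intervention is required, and covers a temporary catheter as well as CIC.
- The scale is assumed. Parent-study entry excluded men with PVR of 100 mL or more, and the safety set contains only men who completed 24 weeks, so the true number could be very small. If sites mixed the readings, the count would fall between the two columns.
- The study has no formal hypotheses, so no test turns on the count.

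**Conclusion.** The definition is ambiguous for one narrow group: PVR of 300 mL or more with catheter intervention judged not required. The lead-in excludes these men from the retention AESI; criterion (a) can be read to include them. Neither the other protocol sections nor the SAP resolves this.

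The consequence is confined to the retention AESI count and to whether the 72-hour report is triggered. One to six such men in 300, an assumed range, would move the incidence by 0.3 to 2.0 percentage points. The firmer part of the finding needs no assumption: the protocol acts on 300 mL, the SAP's PVR categories skip that value, and no any-time count is planned. The change is worth making because it is cheap, not because the safety conclusion is shown to be at risk.

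**What to change.** The sponsor should reconcile the lead-in of Protocol 8.4.6 with criterion (a) and tell sites which is meant. Which clinical rule is right is not for this review to say.

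In SAP 7.3 and 7.7, report the number and percentage of subjects with:

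1. an investigator-reported urinary retention AE;
2. any PVR ≥ 300 mL on or after the first vibegron dose in either study, at any scheduled, unscheduled or withdrawal assessment;
3. either.

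Row 1 still depends on the reading. Row 3 does not: the readings differ only among men with PVR ≥ 300 mL, and row 2 captures all of them. Also add a 300 mL cut to the PVR categories, to match the protocol's own threshold.

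The cost is a clarification to sites, two table rows beyond the planned count, and one more PVR category. PVR is already collected, so no new data are needed. The price to the sponsor is that the reported retention figure may look less favourable.

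### Read literally, a catheterization for inability to void with no PVR value on record is not counted in the urinary-retention AESI; SAP 7.3 should show a supplementary row that counts it

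*Protocol*

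**What the plan says.** Protocol 8.4.6 lists events consistent with urinary retention as an AESI and then restricts when the term may be used: "An AE of urinary retention should only be recorded when a subject has a raised PVR that requires intervention with clean intermittent catheterization (CIC", with temporary placement of a urinary catheter as the alternative. Two criteria follow:

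- Criterion (a), on volume alone: "subject has a PVR of ≥ 300 mL (regardless of symptoms), OR"
- Criterion (b), on volume together with symptoms: "subject has a PVR ≥ 200 mL and < 300 mL and the subject reports associated symptoms". The symptoms are bladder fullness or inability to void, and the investigator must judge that they need CIC.

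A Note sends other cases to an AE of residual urine volume, where "the raised PVR is clinically significant but does not fulfill the above definition for urinary retention". Protocol 2.4.2 confirms the status of this section: "Prespecified definitions of urinary retention and other AESIs are provided in the Adverse Event of Special Interest section".

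On measurement, Protocol 8.3.3 says: "The PVR assessment will be performed via ultrasound at the visits indicated in the Schedule of Assessments". In the extension these are Weeks 28, 36 and 52 (or early withdrawal). The Week 24 value is carried over from the parent study, and Week 44 is a telephone contact without PVR.

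On other routes, Protocol 8.4.5 says that "any events of bladder obstruction should be collected as AEs", with no PVR condition.

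SAP 7.3 repeats the AESI category "Adverse events consistent with urinary retention" and summarizes AESIs by the protocol's categories. SAP 5.5 codes procedures and lists them by subject, but does not tabulate them or link them to an AESI.

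Protocol 7.1 makes any AE of urinary retention a reason to stop study drug, and 8.4.6 repeats that such subjects are withdrawn.

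**The concern.** Retention is the example the protocol synopsis gives of the safety needs particular to men with BPH. The study has a single treatment, no concurrent control in the extension and no formal hypothesis, so the observed number of retention events is itself the evidence on this risk.

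The recording rule needs a number. A man who cannot void between visits and is catheterized at another facility may reach the investigator as a completed event, perhaps first reported at the Week 44 call, with no PVR in the available records. A value from before catheterization cannot be obtained afterwards. If the investigator follows 8.4.6 as written, the event goes under a different term. A reader of the AESI table would then see a retention count that omits a man catheterized for being unable to void.

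**Working it through.** The documents contain no figure to reproduce for this point, so the check sets the rules side by side.

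**Step 1. Which catheterized events can carry the retention term?**

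| Catheterized event | Result under Protocol 8.4.6 | In the retention AESI by the protocol definition? |
|---|---|---|
| PVR of 300 mL or more on record | criterion (a) | Yes |
| PVR from 200 to under 300 mL, with symptoms judged to need CIC | criterion (b) | Yes |
| PVR on record, neither criterion met | residual urine volume, if clinically significant | No, by design |
| Inability to void, no PVR value on record | neither criterion can be shown; the Note also presupposes a raised PVR | No; no rule covers it |

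The last row is the gap. Inability to void appears only inside criterion (b), joined to a PVR range, so it never qualifies alone. By contrast, the hypertension AESI in the same section has a criterion that needs no reading: starting or increasing antihypertensive medication. Retention has no equivalent.

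**Step 2. Does another protocol rule bring the event back?** Appendix 3 says that when a procedure is performed, the AE is the condition that led to it, and that a diagnosis is preferred to signs or symptoms. For an unmeasured acute retention, both point towards the term that 8.4.6 withholds. Section 8.4.5 captures the event, but as bladder obstruction. The three sections do not agree on how to record it.

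**Step 3. Does the SAP bring it back?** SAP 7.3 defers to the protocol's AESI categories and gives no list of retention terms. SAP 5.5 puts a catheterization in a listing only. The PVR summary in SAP 7.7 cannot help, because these events have no PVR value.

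**Step 4. Direction.** Let N be the number of catheterized retention events during vibegron exposure that either meet criterion (a) or (b) or have no PVR value. Let m be those with no PVR value that are reported under another term. The protocol-defined count is N − m. Since m ≥ 0, the count is never too high by this route and is too low whenever m > 0.

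**Step 5. Size.** Neither N nor m, nor any rate from which to derive them, is in the documents. From Day 169 the intervals between scheduled PVR days are 197 − 169 = 28, 253 − 197 = 56 and 365 − 253 = 112 days. The last contains only the telephone contact. These intervals show that an event can easily fall between scans. They do not estimate m, because 8.4.6 does not require the PVR to come from a scheduled scan.

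**The case against.** The strongest reply is that the gap is narrow and the event is not lost.

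- **Source of the PVR.** Nothing in 8.4.6 ties the value to a scheduled visit or to the protocol ultrasound. Unscheduled visits are allowed (Protocol 4.1), and the investigator must arrange medically indicated supplemental measurements (8.4.3). Criterion (b) itself expects a PVR in a man unable to void. This stands. A reader might infer from the sparse PVR schedule that most acute retention would be missed, or try to size the loss from the schedule. The documents do not support that: the gap covers only events with no PVR value from any source. Whether a volume drained by catheter counts as a PVR is not stated.
- **Visibility.** The event still enters the TEAE tables by SOC and preferred term, the serious-TEAE tables if serious, and the procedure listing. This stands, so a reading that such cases vanish from safety reporting would be wrong. It does not repair the AESI count, because a reader would have to reassemble the cases from other terms and a listing.
- **Breadth of the category.** The AESI heading speaks of events consistent with retention, so a coder could place a catheterized obstruction there. That is possible, but neither document gives a rule that ensures it.
- **Purpose of the restriction.** The word only can be read as keeping a merely raised PVR from being called retention. That is a fair reading of its purpose, but it leaves the case with no PVR value unaddressed.

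**Conclusion.** The point holds in a limited form. Followed literally, Protocol 8.4.6 together with SAP 7.3 leaves a catheterization for inability to void with no PVR value outside the retention AESI. The effect can only lower the retention count. Its size cannot be computed, and it may be zero if every such event has a bladder volume on record.

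The conclusion assumes that investigators apply the recording rule as written and that AESI assignment follows it. The SAP safety analysis covers all vibegron exposure in both studies (SAP 3.1.2). The parent study's recording rule is not in these documents, so the conclusion is established for events recorded under this protocol.

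A reader might infer that the remedy is to loosen the recording rule in 8.4.6 as a mere counting change. That does not follow: under 7.1 and 8.4.6 the same AE term leads to discontinuation and withdrawal, so new wording could change who stops treatment.

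**What to change.** In SAP 7.3, before database lock, report the retention AESI in two rows:

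1. Events that meet the protocol definition, as now planned.
2. Row 1 plus any TEAE of urinary retention, inability to void or bladder obstruction that was managed with bladder catheterization, identified from the AE and concomitant-procedure data, with or without a PVR value.

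Show both rows beside each other in the safety conclusion. If they agree, the protocol-defined count is better supported. If they differ, the reader sees by how much.

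The cost is a short SAP paragraph and one extra row built from data that the SAP already treats as collected and coded. Row 2 may include a few catheterizations that were not retention, so the stated rate may be slightly less favourable.

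No protocol rewording is proposed. The sponsor should reconcile the 8.4.6 recording rule with 7.1 (discontinuation), with 8.4.5 (bladder obstruction collected as AEs) and with the Appendix 3 rule that the condition leading to a procedure is the AE. The supplementary row does not depend on how that is resolved.
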